**Statistical Method:**

All immunogenicity data collected at scheduled and unscheduled visits will be included in the listings, but only results collected as scheduled visits will be included in the summary tables.

All results will be presented descriptively and summarized by treatment arms.

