4.2 Scientific Rationale of Trial Design

This study is designed as a standard double-blind placebo-controlled single administration, dose-ranging study to evaluate the effect of 2 different doses (high and medium dose) of VXA-GII.4-NS plus VXA-G1.1-NN in the target population, compared with placebo.

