11.4.3 Analysis of Primary, Secondary, and Exploratory Immunogenicity and Endpoints

Immunogenicity will be summarized according to the treatment group to which the subject was randomized.

Immunogenicity samples will be drawn for all subjects. Immunogenicity analyses will be based upon results from appropriately sized subsets of samples, according to the purpose. The statistical analysis of immunogenicity results will be primarily based on the evaluable immunogenicity sets.

An additional analysis will be performed based on the all-available sets if there is a large enough difference in sample size between the all-available immunogenicity set and the evaluable immunogenicity set.

Immunogenicity will be summarized by the total set (active vs. placebo). For all endpoints, all measures will be analyzed comparing the two active vaccine groups. The immunogenicity set will be used for this analysis. All results will be presented descriptively and summarized by treatment groups.

Endpoint	Statistical Analysis Methods
Primary (Key Immunogenicity Endpoints measured from Day 1 through Day 29)	Serum and breastmilk VP1 specific IgA for both GI.1 and GII.4 by Meso Scale Discovery will be summarized descriptively through the active period (4 weeks post dose).
Secondary (measured through Day 180)	Serum VP1 specific IgA and IgG for both GI.1 and GII.4 by Meso Scale Discovery will be summarized descriptively through 6 months post dose. Serum Blocking titers 50 (BT50) (GI.1 and GII.4) by Histo-blood group antigen (HBGA) assay will be summarized descriptively through 6 months post dose. Breastmilk VP1 specific IgA for both GI.1 and GII.4 by Meso Scale Discovery will be summarized descriptively through 6 months post dose.
Exploratory	For specific exploratory immunogenicity endpoints please refer to Section 8.2-Immunogenicity Assessments- Exploratory Immunogenicity Assessments.

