## 2.3 Endpoints

### 2.3.1 Primary endpoints

- **Safety:**
  - Frequency, duration, and severity of solicited symptoms of reactogenicity (local, systemic) for 1 week following each dose of study drug.
  - Frequency, duration, and severity of unsolicited treatment-emergent adverse events (TEAEs), serious AEs (SAEs), adverse events of special interest (AESIs), and new onset of chronic illness (NOCIs) through the active period (4 weeks post last dose).
- **Immunogenicity:**
  - Serum VP1 specific (GI.1 and GII.4) IgA through the active period measured by Meso Scale Discovery (MSD) assay by dose level
    - Geometric mean concentration (GMC) at Day 1, Day 8 and Day 29
    - Geometric mean fold rise (GMFR) from Day 1 to Day 8 and from Day 1 to Day 29
    - The number of subjects in each dose group that had a 2-fold, 3-fold and 4-fold GMC rise or greater in serum VP1 specific IgA (GI.1 and GII.4) between Day 1 and any other timepoint.
  - Breast Milk VPI specific (GI.1 and GII.4) IgA through the active period measured by Meso Scale Discovery (MSD) assay by dose level
    - Geometric mean concentration (GMC) at Day 1, Day 8, and Day 29
    - Geometric mean fold rise (GMFR) from Day 1 to Day 8, and from Day 1 to Day 29

- The number of subjects in each dose group that had a 2-fold, 3-fold and 4-fold GMC rise or greater in breast milk VP1 specific IgA (GI.1 and GII.4) between Day 1 and any other timepoint.

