### 3.3 Inferential Analyses

No formal hypothesis testing is planned.

Descriptive statistics will be used to summarize the safety and immunogenicity data.

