**Geometric Mean Concentration (GMC) or Geometric Mean Titer (GMT) and Fold Change from Baseline**

- Serum VP1 specific (GI.1 and GII.4) IgA, Serum VP1 specific (GI.1 and GII.4) IgG, GMCs with 95% CI, and their respective fold changes from baseline will be reported.
- Breast Milk VPI specific (GI.1 and GII.4) IgA GMCs with 95% CI, and their respective fold changes from baseline will be reported.
- Serum Blocking titers 50 (BT50) (GI.1 and GII.4), GMTs with 95% CI, and their respective fold changes from baseline will be reported.
- The 2-fold, 3-fold and 4-fold rise will be summarized for all the above immunogenicity endpoints.

Geometric means and its two-sided 95% Confidence Interval (CI) will be presented in original scale after back transformation of data.

Antibody responses over time will be shown graphically using a bar chart by the 2 active vaccine arms for:

- Serum VP1 specific (GI.1 and GII.4) IgA, Serum VP1 specific (GI.1 and GII.4) IgG with geometric mean concentration and their associated confidence intervals applied to the log transformed responses.
- Breast Milk VPI specific (GI.1 and GII.4) IgA with geometric mean concentration and their associated 95% confidence intervals applied to the log transformed responses.
- Serum antibody blocking titers 50 (BT50) (GI.1 and GII.4) with geometric mean titer and their associated 95% confidence intervals applied to the log transformed responses.

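### SAP section 14 specifies no between-arm immunogenicity estimate, although Protocol 11.4.3 says the two active groups will be compared; a baseline-adjusted ratio with a 95% CI would supply it from data already planned

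*SAP*

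**What the plan says.** Protocol v2.0 section 4.2 gives the purpose of the design as to "evaluate the effect of 2 different doses (high and medium dose) of VXA-GII.4-NS plus VXA-G1.1-NN in the target population, compared with placebo". Section 11.4.3 adds two statements about immunogenicity: "Immunogenicity will be summarized by the total set (active vs. placebo" (closing bracket omitted), and "For all endpoints, all measures will be analyzed comparing the two active vaccine groups". The same paragraph ends by calling all results descriptive.

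SAP section 14, under Statistical Method, says "All results will be presented descriptively and summarized by treatment arms". The GMC and GMT formulas that follow are defined within each arm, and fold rise is defined per subject against Day 1. The SAP puts a 95% CI on geometric means and counts subjects with 2-, 3- and 4-fold rises. Every immunogenicity table in SAP section 18 is a by-arm summary. The primary milk responder endpoint counts a "GMC rise or greater in breast milk VP1 specific IgA (GI.1 and GII.4) between Day 1 and any other timepoint". For figures, SAP section 14 says "Antibody responses over time will be shown graphically using a bar chart by the 2 active vaccine arms".

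SAP section 3.3 states "No formal hypothesis testing is planned". SAP section 15 lists the added fold-rise thresholds and the reduced BT50 visits as changes to the planned analysis. It does not list any removal of the comparison between active groups.

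**The concern.** A rise from Day 1 within one arm combines the vaccine effect with anything else that changes over the same weeks: natural exposure, stage of lactation and assay drift. Infants may be from just over 30 days to 11 months old at dosing, so lactation stage will vary widely. Milk IgA is tabulated per µg of total IgA. That may absorb part of the lactation change, but it also means that a shift in the denominator moves the result. The concurrent placebo arm deals with these shared influences, but the SAP defines no estimate that uses it this way.

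The same gap affects dose. This is a dose-ranging trial with two active arms of 30, and the SAP has no estimate or interval for high versus medium. The CSR could give a GMFR and a responder rate for milk IgA, the response that the primary objective singles out as most critical, without saying how far the doses differ from each other or from placebo. SAP section 1 requires unplanned analyses to be labelled as such in the CSR, so a contrast added after unblinding would be reported as post hoc.

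**Working it through.** **What the plan specifies and what it does not**

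| Item | Protocol v2.0 | SAP |
|---|---|---|
| High v medium | 11.4.3: to be compared on all measures | No estimate or interval |
| Active v placebo | 4.2 and 11.4.3: stated descriptively | By-arm columns and a pooled active column (3.7); no contrast |
| Treatment differences, LS-means | – | 3.1 gives decimal places only; no model, covariate or table produces them |
| Declared as a change | – | Not in section 15 |

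**Are the data there?** The Schedule of Activities takes a Day 1 sample of serum and milk from every woman in every arm. Post-dose serum is taken at Days 8, 29 and 180, and milk at Days 8, 29, 60 and 180. There is no serum at Day 60. SAP section 15 limits serum BT50 to Days 1 and 29. A baseline-adjusted contrast is therefore possible at those visits and no others.

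**The plan's own figure.** 30 + 30 + 16 = 76, as stated in Protocol 11.1 and SAP 2.4. The documents give no SD, correlation, power or target precision, so nothing else can be reproduced.

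**Illustrative precision.** Assumed: log10 SD 0.5 and correlation 0.7 between the Day 1 and post-dose values. The 95% CI is the ratio multiplied and divided by

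10^[ t × 0.5 × k × √(1/n₁ + 1/n₂) ]

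where k = 1 for the unadjusted post-dose ratio, k = √(2(1 − 0.7)) = 0.775 for the ratio of GMFRs, and k = √(1 − 0.7²) = 0.714 for ANCOVA.

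- One dose v placebo (30 v 16): t(44) = 2.015 and √(1/30 + 1/16) = 0.310. The exponents are 0.312, 0.242 and 0.223, giving factors of 2.05, 1.74 and 1.67.
- High v medium (30 v 30): t(58) = 2.002 and √(2/30) = 0.258. The exponents are 0.258, 0.200 and 0.185, giving factors of 1.81, 1.59 and 1.53.

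On the log scale ANCOVA is 1 − 0.714 = 29% narrower than the unadjusted ratio and 1 − 0.714/0.775 = 8% narrower than the GMFR ratio. Over SD 0.3 to 0.6 with correlation 0.5, and 72 residual degrees of freedom from a three-arm model, the ANCOVA factor runs from 1.36 to 1.85 for high v medium and from 1.45 to 2.09 for one dose v placebo.

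**Responders by chance.** Suppose there is no true change, visit errors are independent with log10 SD s, and all visits share one baseline. At one visit the chance of a rise of at least 2-fold is 1 − Φ(0.301 / (s√2)). For s = 0.20 this is 1 − Φ(1.064) = 14%. The chance at either of two visits was simulated because the visits share a baseline:

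| Assumed s | One visit | Either of Days 8 and 29 |
|---|---|---|
| 0.15 | 8% | 13% |
| 0.20 | 14% | 23% |
| 0.27 | 22% | 33% |

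The value 0.27 is the one consistent with the precision assumptions above: 0.5 × √(1 − 0.7) = 0.27.

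**The case against.** The strongest reply is that the plan is descriptive by design. Protocol 11.1 gives placebo's role as safety comparison, section 4.2 is general rationale rather than an analysis instruction, and no testing is planned. Placebo and pooled active columns will stand beside each dose, so drift in placebo will be visible. All of that stands. It means that a reader who infers a broken promise of a formal test against placebo goes beyond the documents. It does not supply the comparison of active groups in Protocol 11.4.3, and two by-arm intervals side by side do not give an interval for the ratio.

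Several other inferences are tempting but not supported:

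- *Fold rises have no CI.* A GMFR is a geometric mean, so the CI sentence in SAP 14 can be read to cover it. It should say so.
- *Placebo is excluded from the figures.* The sentence about two active arms conflicts with SAP 3.7, whose labels for figures include placebo, and with figure titles worded by treatment arm. This is an inconsistency to resolve, not a settled exclusion.
- *The primary milk responder endpoint spans four visits.* It sits under the active period, so Days 8 and 29 are the natural reading. The chance rate for any of four visits (about 34.5% at s = 0.20) is not the primary case. The wording is also the protocol's own, and the SAP already tabulates fold rise visit by visit.

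It is also fair to say that ANCOVA gains only 8% over a plain ratio of GMFRs. Having some prespecified contrast matters more than which of the two is chosen.

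**Conclusion.** The point holds as a gap between the protocol's stated descriptive comparison and the SAP's outputs. It is firm for high versus medium, where Protocol 11.4.3 is explicit and the SAP has nothing to match. It is softer for each dose versus placebo, where the protocol's wording is descriptive and placebo's stated role is safety. The formatting rules in SAP 3.1 do not close the gap, because no analysis generates the quantities they format.

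Under the illustrative assumptions, adjusted ratios would carry 95% CI factors of about 1.53 (high v medium) and 1.67 (dose v placebo), and 13% to 33% of women with no true change would count as 2-fold milk responders over two visits. These sizes rest entirely on assumed SDs and a correlation, and on full arms of 30, 30 and 16. SAP 14 allows analysis of subsets of samples, so the numbers assayed may be smaller. The intervals are wide enough that the result should be presented as estimation. This is an improvement that should be made, not a flaw that invalidates the planned summaries.

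**What to change.** Amend SAP section 14 and the table list before unblinding:

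1. For each strain, fit an ANCOVA of the log10 result on arm and log10 Day 1 value. Report geometric mean ratios with 95% CIs and no p-values for high v medium, medium v placebo and high v placebo. Use only visits sampled and assayed: serum IgA and IgG at Days 8, 29 and 180; milk IgA at Days 8, 29, 60 and 180; serum BT50 at Day 29. Name Day 29 as the main visit.
2. State that the 95% CI also applies to GMFR.
3. Keep the protocol's milk responder endpoint and say that its primary version covers Days 8 and 29. Add Clopper-Pearson CIs per arm and, as a supplement, the Day 29 difference from placebo with a Newcombe or Miettinen-Nurminen CI.
4. Show placebo in the figures, so that SAP 14 agrees with SAP 3.7 and the figure list.
5. Record the added contrasts in SAP section 15.

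The cost is SAP wording and one extra table per analyte. No new samples or visits are needed, the protocol-defined endpoint is unchanged, and the plan remains free of hypothesis tests.

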**Definitions for GMC, GMT and Fold Rises**

**GMC** =  $10^{\frac{1}{N} \sum \log_{10}(C_i)}$  where  $i = 1, 2, \dots, N$

where N denotes the number of subjects within each treatment arm and  $C_i$  is the per subject immunogenicity concentration.

**Fold Rise (Flr)** =  $[CD8, CD29, CD60 \text{ or } CD180]/[CD1]$ .

CD8, CD29, CD60 and CD180 are the per subject immunogenicity concentration on Day 8, Day 29, Day 60, and Day 180 respectively.

CD1 = per subject immunogenicity concentration on Day 1 (pre-vaccination)

Flr is the fold rise per subject.

The fold change will be calculated per subject by dividing the concentration (original scale) on Day 8, 29, 60 and 180 with concentration at baseline (Day 1).

**GMT** =  $10^{\frac{1}{N} \sum \log_{10}(T_i)}$  where  $i = 1, 2, \dots, N$

where N denotes the number of subjects within each treatment arm and  $T_i$  is the per subject immunogenicity titer.

Fold Rise (Flr) =  $[TD8, TD29 \text{ or } TD180]/[TD1]$ .

TD8, TD29 and TD180 are the per subject immunogenicity titers on Day 8, Day 29 and Day 180 respectively.

TD1 = per subject immunogenicity titers on Day 1 (pre-vaccination)

Flr is the fold rise per subject.

The fold change will be calculated per subject by dividing the titer (original scale) on Day 8, 29 and 180 with titer at baseline (Day 1).

$\geq x$  -Fold Rise represents the percentage of subjects with at least a x-Fold Rise compared to pre-vaccination dosing (Day 1), where  $x=2,3$  and 4.

**Geometric Mean Concentration (GMC) or Geometric Mean Titer (GMT) and Fold Change from Baseline**

- Serum VP1 specific (GI.1 and GII.4) IgA, Serum VP1 specific (GI.1 and GII.4) IgG, GMCs with 95% CI, and their respective fold changes from baseline will be reported.
- Breast Milk VPI specific (GI.1 and GII.4) IgA GMCs with 95% CI, and their respective fold changes from baseline will be reported.
- Serum Blocking titers 50 (BT50) (GI.1 and GII.4), GMTs with 95% CI, and their respective fold changes from baseline will be reported.
- The 2-fold, 3-fold and 4-fold rise will be summarized for all the above immunogenicity endpoints.

Geometric means and its two-sided 95% Confidence Interval (CI) will be presented in original scale after back transformation of data.

Antibody responses over time will be shown graphically using a bar chart by the 2 active vaccine arms for:

- Serum VP1 specific (GI.1 and GII.4) IgA, Serum VP1 specific (GI.1 and GII.4) IgG with geometric mean concentration and their associated confidence intervals applied to the log transformed responses.
- Breast Milk VPI specific (GI.1 and GII.4) IgA with geometric mean concentration and their associated 95% confidence intervals applied to the log transformed responses.
- Serum antibody blocking titers 50 (BT50) (GI.1 and GII.4) with geometric mean titer and their associated 95% confidence intervals applied to the log transformed responses.

## 15. CHANGES TO THE PLANNED ANALYSIS

Changes to the planned analyses of the protocol and/or to the planned analyses from the SAP will be documented in the Statistical Report and in the Clinical Study Report (CSR).

Below is a description of changes made to the planned analysis for the Immunogenicity assessments:

- Calculation of 2-fold, 3-fold and 4-fold in GMCs and 2-fold, 3-fold and 4-fold in GMTs added in the primary and secondary immunogenicity endpoints.

Protocol Section(s), Description	Change in SAP
3.2.2. Immunogenicity Serum Blocking titers 50 (BT50) (GI.1 and GII.4) through 6 months after study drug dose measured by Histo-blood group antigen (HBGA) assay by dose level ▪ Geometric mean titer (GMT) at Day 1, Day 8, Day 29, and Day 180 ▪ Geometric mean fold rise (GMFR) from Day 1 to Day 8, from Day 1 to Day 29, and from Day 1 to Day 180	Serum Blocking titers 50 (BT50) (GI.1 and GII.4) through 6 months after study drug dose measured by Histo-blood group antigen (HBGA) assay by dose level ▪ Geometric mean titer (GMT) at Day 1 and Day 29 ▪ Geometric mean fold rise (GMFR) from Day 1 to Day 29

**16. INTERIM AND FINAL ANALYSIS**

A principal statistical analysis will be performed after all subjects have completed the active period of the study up to Day 29 post-vaccination, the subject database has been locked, the analysis set of populations will be approved, and the study will be unblinded except the medical monitoring and pharmacovigilance team including anyone at the Sponsor, CRO and sites(s). The principal Clinical Study Report (CSR) will be written after this analysis. If any exploratory parameters are available, Vaxart will keep them for possible future analysis. A final statistical analysis will be performed after all subjects have completed the long-term follow-up phase of the study up to Day 365 post-vaccination and safety dataset has been locked. An addendum to the principal CSR will be written after this analysis.

The final analysis will be based on the final version of SAP.

**17. SOFTWARE**

- SAS® Version 9.4 or higher (SAS Institute, Cary, North Carolina, USA).

**18. TABLES**

Table Number	Table Title	Population
14.1	Demographics and Other Baseline Characteristics	
14.1.1	Summary of Subject Enrolment and Disposition by Treatment arm	ScS
14.1.2	Summary of Demographics and Baseline Characteristics by Treatment arm	Safety
14.1.3	Summary of Medical/Surgical History by System Organ Class, Preferred Term and Treatment arm	Safety
14.2	Immunogenicity	
14.2.1.1	Summary of Serum VP1 Specific GI.1 and GII.4 IgA (AU/mL) Geometric Mean Concentration and Fold Rise from Baseline at Day 8 by Treatment Arm	Immunogenicity
14.2.1.1a	Summary of Serum VP1 Specific GI.1 and GII.4 IgA (AU/mL) Geometric Mean Concentration and Fold Rise from Baseline at Day 8 by Treatment Arm	Per Protocol
14.2.1.2	Summary of Serum VP1 Specific GI.1 and GII.4 IgA (AU/mL) Geometric Mean Concentration and Fold Rise, from Baseline at Day 29, by Treatment Arm	Immunogenicity
14.2.1.2a	Summary of Serum VP1 Specific GI.1 and GII.4 IgA (AU/mL) Geometric Mean Concentration and Fold Rise, from Baseline at Day 29, by Treatment Arm	Per Protocol
14.2.1.3	Summary of Serum VP1 Specific GI.1 and GII.4 IgA (AU/mL) Geometric Mean Concentration and Fold Rise from Baseline at Day 180 by Treatment Arm	Immunogenicity
14.2.1.3a	Summary of Serum VP1 Specific GI.1 and GII.4 IgA (AU/mL) Geometric Mean Concentration and Fold Rise from Baseline at Day 180 by Treatment Arm	Per Protocol
14.2.2.1	Summary of Breast Milk VP1 Specific GI.1 and GII.4 IgA (RLU/ug of total IgA) Geometric Mean Concentration and Fold Rise from Baseline at Day 8 by Treatment Arm	Immunogenicity
14.2.2.1a	Summary of Breast Milk VP1 Specific GI.1 and GII.4 IgA (RLU/ug of total IgA) Geometric Mean Concentration and Fold Rise from Baseline at Day 8 by Treatment Arm	Per Protocol
14.2.2.2	Summary of Breast Milk VP1 Specific GI.1 and GII.4 IgA (RLU/ug of total IgA) Geometric Mean Concentration and Fold Rise from Baseline at Day 29 by Treatment Arm	Immunogenicity
14.2.2.2a	Summary of Breast Milk VP1 Specific GI.1 and GII.4 IgA (RLU/ug of total IgA) Geometric Mean Concentration and Fold Rise from Baseline at Day 29 by Treatment Arm	Per Protocol
14.2.2.3	Summary of Breast Milk VP1 Specific GI.1 and GII.4 IgA (RLU/ug of total IgA) Geometric Mean Concentration and Fold Rise from Baseline at Day 60 by Treatment Arm	Immunogenicity
14.2.2.3a	Summary of Breast Milk VP1 Specific GI.1 and GII.4 IgA (RLU/ug of total IgA) Geometric Mean Concentration and Fold Rise from Baseline at Day 60 by Treatment Arm	Per Protocol
14.2.2.4	Summary of Breast Milk VP1 Specific GI.1 and GII.4 IgA (RLU/ug of total IgA) Geometric Mean Concentration and Fold Rise from Baseline at Day 180 by Treatment Arm	Immunogenicity

Table Number	Table Title	Population
14.2.2.4a	Summary of Breast Milk VP1 Specific GI.1 and GII.4 IgA (RLU/ug of total IgA) Geometric Mean Concentration and Fold Rise from Baseline at Day 180 by Treatment Arm	Per Protocol
14.2.3.1	Summary of Serum VP1 Specific GI.1 and GII.4 IgG (AU/mL) Geometric Mean Concentration and Fold Rise, from Baseline at Day 8, by Treatment Arm	Immunogenicity
14.2.3.1a	Summary of Serum VP1 Specific GI.1 and GII.4 IgG (AU/mL) Geometric Mean Concentration and Fold Rise, from Baseline at Day 8, by Treatment Arm	Per Protocol
14.2.3.2	Summary of Serum VP1 Specific GI.1 and GII.4 IgG (AU/mL) Geometric Mean Concentration and Fold Rise, from Baseline at Day 29, by Treatment Arm	Immunogenicity
14.2.3.2a	Summary of Serum VP1 Specific GI.1 and GII.4 IgG (AU/mL) Geometric Mean Concentration and Fold Rise, from Baseline at Day 29, by Treatment Arm	Per Protocol
14.2.3.3	Summary of Serum VP1 Specific GI.1 and GII.4 IgG (AU/mL) Geometric Mean Concentration and Fold Rise, from Baseline at Day 180, by Treatment Arm	Immunogenicity
14.2.3.3a	Summary of Serum VP1 Specific GI.1 and GII.4 IgG (AU/mL) Geometric Mean Concentration and Fold Rise, from Baseline at Day 180, by Treatment Arm	Per Protocol
14.2.4.1	Summary of Serum GI.1 and GII.4 Blocking Titers 50 (BT50) Geometric Mean Titer and Fold Rise, from Baseline at Day 29, by Treatment Arm	Immunogenicity
14.2.4.1a	Summary of Serum GI.1 and GII.4 Blocking Titers 50 (BT50) Geometric Mean Titer and Fold Rise, from Baseline at Day 29, by Treatment Arm	Per Protocol
14.3	Safety	
14.3.1	Summary of Concomitant Medications by ATC Class, Preferred Name and Treatment arm.	Safety
14.3.3	Adverse Events	
14.3.3.1.1	Summary of Solicited Symptoms of Reactogenicity Post-Vaccination by Treatment arm	Safety
14.3.3.1.2	Summary of Solicited Symptoms of Reactogenicity continuing beyond Day 8 Post-Vaccination by Treatment arm	Safety
14.3.3.1.3	Summary of Solicited Symptoms of Reactogenicity by Treatment Arm and by Severity from Day 1 to Day 8 Post-Vaccination	Safety
14.3.3.1.4	Summary of Overall Unsolicited Treatment Emergent Adverse Events by Treatment arm, from Day 1 to Day 29 Post-Vaccination.	Safety
14.3.3.1.5	Summary of duration (in days) of Overall Unsolicited Treatment Emergent Adverse Events by Treatment arm, from Day 1 to Day 29 Post-Vaccination	Safety
14.3.3.1.6.1	Summary of Unsolicited Treatment Emergent Adverse Events by System Organ Class, Preferred Term and Treatment arm, from Day 1 to Day 29 Post-Vaccination	Safety
14.3.3.1.6.2	Summary of Unsolicited Treatment Emergent Adverse Events by System Organ Class, Preferred Term, Severity and Treatment arm, from Day 1 to Day 29 Post-Vaccination	Safety

Table Number	Table Title	Population
14.3.3.1.6.3	Summary of Unsolicited Treatment Emergent Adverse Events by System Organ Class, Preferred Term, Relationship and Treatment arm, from Day 1 to Day 29 Post-Vaccination	Safety
14.3.3.1.7.1	Summary of Serious Adverse Events by System Organ Class, Preferred Term and Treatment arm, from Day 1 to Day 29 Post-Vaccination	Safety
14.3.3.1.7.2	Summary of Serious Adverse Events by System Organ Class, Preferred Term, Severity and Treatment arm, from Day 1 to Day 29 Post-Vaccination	Safety
14.3.3.1.7.3	Summary of Serious Adverse Events by System Organ Class, Preferred Term, Relationship and Treatment Arm, from Day 1 to Day 29 Post-Vaccination	Safety
14.3.3.1.7.4	Summary of Serious Adverse Events by System Organ Class, Preferred Term and Treatment Arm, From Day 30 to Day 365 Post-Vaccination	Safety
14.3.3.1.7.5	Summary of Serious Adverse Events by System Organ Class, Preferred Term, Severity and Treatment Arm, from Day 30 to Day 365 Post-Vaccination	Safety
14.3.3.1.7.6	Summary of Serious Adverse Events by System Organ Class, Preferred Term, Relationship and Treatment Arm, from Day 30 to Day 365 Post-Vaccination	Safety
14.3.3.1.8.1	Summary of New Onset of Chronic Illness by System Organ Class, Preferred Term and Treatment arm, from Day 1 to Day 29 Post-Vaccination	Safety
14.3.3.1.8.2	Summary of New Onset of Chronic Illness by System Organ Class, Preferred Term, Severity and Treatment arm, from Day 1 to Day 29 Post-Vaccination	Safety
14.3.3.1.8.3	Summary of New Onset of Chronic Illness by System Organ Class, Preferred Term, Relationship and Treatment Arm, from Day 1 to Day 29 Post-Vaccination	Safety
14.3.3.1.8.4	Summary of New Onset of Chronic Illness by System Organ Class, Preferred Term and Treatment Arm, from Day 30 to Day 365 Post-Vaccination	Safety
14.3.3.1.8.5	Summary of New Onset of Chronic Illness by System Organ Class, Preferred Term, Severity and Treatment Arm, from Day 30 to Day 365 Post-Vaccination	Safety
14.3.3.1.8.6	Summary of New Onset of Chronic Illness by System Organ Class, Preferred Term, Relationship and Treatment Arm, from Day 30 to Day 365 Post-Vaccination	Safety
14.3.3.1.9.1	Summary of Adverse Event of Special Interest by System Organ Class, Preferred Term and Treatment Arm, from Day 1 to Day 29 Post-Vaccination	Safety
14.3.3.1.9.2	Summary of Adverse Event of Special Interest by System Organ Class, Preferred Term, Severity and Treatment Arm, from Day 1 to Day 29 Post-Vaccination	Safety
14.3.3.1.9.3	Summary of Adverse Event of Special Interest by System Organ Class, Preferred Term, Relationship and Treatment Arm, from Day 1 to Day 29 Post-Vaccination	Safety
14.3.3.1.9.4	Summary of Adverse Event of Special Interest by System Organ Class, Preferred Term and Treatment Arm, from Day 30 to Day 365 Post-Vaccination	Safety

Table Number	Table Title	Population
14.3.3.1.9.5	Summary of Adverse Event of Special Interest by System Organ Class, Preferred Term, Severity and Treatment Arm, from Day 30 to Day 365 Post-Vaccination	Safety
14.3.3.1.9.6	Summary of Adverse Event of Special Interest by System Organ Class, Preferred Term, Relationship and Treatment Arm, from Day 30 to Day 365 Post-Vaccination	Safety
14.3.5	Other Safety	
14.3.5.1.1	Summary of Vital Signs by Treatment arm	Safety
14.3.5.1.2	Summary of Clinical Assessments of Vital Signs by Treatment arm	Safety

---

